Placebo-controlled Randomized Clinical Trial: tDCS to Prevent Relapse in Alcohol Use Disorder

NCT ID: not yet assigned

Date: 25 February 2021

1. Background

Despite the available treatments in place, patients with alcohol use disorder (AUD) continue to relapse after treatment (Manning et al., 2016, 2020; Noël et al., 2021). For the past twenty years, neuromodulations techniques and their mechanisms, including transcranial direct current stimulation (tDCS), have been largely investigated in medical research (Ekhtiari et al., 2019; Fertonani & Miniussi, 2017; Nitsche et al., 2003; Philip et al., 2017). The tDCS is a neuromodulation tool acting by a current of maximum 2 mA delivered by two electrodes: the anode increases the cortical excitability (depolarizing the membrane potential on neurons) while the cathode inhibits the cortical excitability (hyperpolarizing the membrane potential) (Zhao et al., 2017).

The tDCS has shown interesting effects in patients with AUD when applied to the dorsolateral prefrontal cortex (dlPFC). The dlPFC is involved in decision-making, inhibitory control and working memory (Bechara 2005), as well as attentional bias (Bechara 2005), as well as attentional bias (Knight et al., 2020). The dlPFC appears to be hypoactivated in patients with AUD, which translates in impaired inhibition control and impaired attention to alcohol-related stimuli (Goldstein & Volkow, 2011).

Currently in the scientific literature we can find many studies focusing on craving but only few investigating relapse's mechanisms and treatment (Coles et al., 2018; Trojak et al., 2017). Nevertheless, two studies have shown that 10 sessions of tDCS on dlPFC (2mA, anode on the right, cathode on the left) allow a decrease in relapse's rate (3 and 6 months after the intervention) (Klauss et al., 2014, 2018). Among a sample of 33 hospitalized patients, eight patients in the active

tDCS condition were still abstinent after 6 months follow-up, compared to two in the sham tDCS condition (50% versus 11.8% of the respective samples).

Meta-analyses have shown a moderate effect of tDCS reducing craving (Chen et al., 2020; Hone-Blanchet et al., 2015; Jansen et al., 2013; Kang et al., 2019; Luigjes et al., 2018; Mostafavi et al., 2020; Sauvaget et al., 2015). The latest recommendations are to place the anode on the right CPFDL and the cathode on the left CPFDL, for a minimum of 5 sessions of 20 minutes at 2 mA (Fregni et al., 2020; Lefaucheur et al., 2017).

We conducted a first clinical trial at Unit 72 Addictology of CHU Brugmann between 2017 and 2020 (reference: CE 2017/117), which was funded by the King Baudouin Foundation (ref: 2016-J1130650-206500) and then by the Brugmann Foundation (fund 2020-2021) (article in writing, pre-registered: <https://clinicaltrials.gov/ct2/show/NCT03447054>). The study had a design with 2x2 conditions combining 5 sessions of (A) tDCS on the dlPFC (anode on the right and cathode on the left, active 2mA vs sham 0mA) simultaneously to (B) an inhibition cognitive training (ICT) type Go/Nogo (specific vs non-specific). The specific ICT consisted to associate the Nogo with alcohol images and Go with sports images. There were also neutral images associated with 50% of Go. While non-specific training had only neutral images. Results showed a decrease in relapse's rate two weeks after treatment due to real tDCS combined with ICT. Moreover, we found out that real tDCS combined with specific ICT was more effective than real tDCS combined nonspecific ICT. Nevertheless, we did not find any significant effect on other clinical variables [craving (visual analog scale), symptoms of depression (BDI-II), anxiety (STAI-A), work memory (OSPA) and inhibition (Stop signal task)].

Following these results, one question still remains: Should tDCS be combined with ICT in order to be effective? To answer this question, we are conducting a new clinical trial with 5 sessions of tDCS on CPFDL (20minutes, anode on the right, left cathode) without an ICT. This study follows the same tDCS configuration as the previous one and takes place within the same multidisciplinary framework of treatment in order to compare our data.

2. HYPOTHESES

For patients with AUD, the intervention of five sessions of tDCS during a detoxification:

- decreases the relapse rate 2 weeks after the treatment;
- decreases patient craving;
- improves depression and anxiety;
- strengthens inhibitory capacities.

3. PROTOCOL

3.1. Patients

This is a clinical trial that is part of an alcohol detoxification cure at Unit 72 Addictology of CHU Brugmann. The idea is to add a neuromodulation intervention to the initial management, multidisciplinary and psycho-bio-social. This will be a randomized, sham-controlled, single-blind study.

A total of 60 subjects will be recruited according to the inclusion and exclusion criteria. They will be randomly divided into two groups: the 'active' group (A) that will benefit from tDCS stimulation and the 'sham' group (S).

Exclusion criteria:

- Personal history of epilepsy;
- Have metal head implants that counter-indicate electrical stimulation;
- Diagnosis of chronic psychotic disorder, schizophrenia or bipolar type 1 disorder;
- Use of alcohol or other illicit substances during the experiment;
- Hair incompatible with neuromodulation.

[figure not shown]

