3.2. Procedure

During the first two weeks of hospitalization, the study will be offered to patients. If they accept, a first semi-structured interview will be organized to explain the study, sign the informed consent, collect more information and verify the inclusion and exclusion criteria. During this interview, the demographic characteristics (age, sex and level of education), history with alcohol (number of years of dependence, number of previous treatment, etc.), frequency and amount of alcohol consumed before treatment, psychiatric history, etc. The DSM 5 criteria will be verified, and patients will complete these questionnaires in French version: *Alcohol Use Disorder Identification Test (AUDIT)*, *Impulsivity Behavior Scale (UPPS-P)* and *Trait Anxiety Inventory (STAI-B)*.

From Monday to Friday of the third week of hospitalization, patients will receive the procedure. Five consecutive 20 minute days of tDCS, either active or sham. Before and after each session, the tie will be measured using analog visual scales. To measure the effects of tDCS, on the Friday preceding (T1) and the Monday following (T2) the intervention week,

patients will respond to a battery of questionnaires and cognitive tasks during the recording of evoked potentials (via an electroencephalogram). T1 and T2 will each last approximately one hour.

Figure 1: Study plan. Day 1 is theoretically the first day of hospitalization and the procedure takes place between Day 15 and 19.

In order to observe whether specific neural changes underlie relapse and abstinence, evoked potentials will be acquired for each participant at two points, before the start of the stimulation by tDCS and once the five sessions have been completed.

Once hospitalization is complete, patients will be followed by telephone call to find out the status of their abstinence and/or alcohol consumption. The call will be made via Unit 72 personnel.

Recruitment would start if possible at the end of March 2021 for a period of 12 months. Based on our estimates based on the performance of the previous study, five patients will be recruited per month.

[figure not shown]
3.3. tDCS

During the neuromodulation session, the patient will watch nature documentaries, cut into 5 episodes of 20 minutes.

The configuration of tDCS is based on recommendations in the literature (Fregni et al., 2020; Lefaucheur et al., 2017).

- 5 sessions of bilateral stimulation of the dlPFC;

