- Electrode setup: the anode right on F4 and cathode left on F3, according to international system 10-20 for EEG;
- Administration of 2mA of current for 20 min;
- Sham group: 0 mA for 20 min, 2 mA for the first 15 and last seconds.

Figure 2: Localization of the anode (red) and the cathode (blue) over the dlPFC.

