3.4. Measures

Primary dependent variables :

Relapse and total abstinence measured at several defined times: two weeks, one month, three months, six months and one year after treatment..

Secondary dependent variables:

- Craving measured before and after each tDCS session via visual analog scales, such as Likert -100 to +100, as well as the *Alcohol Urge Questionnaire* (AUQ) with 8 items. Craving will also be measured in T1 and T2 through the *Craving Experience Questionnaire* (CEQ);

- Symptoms of depression with the *Beck Depression Inventory* (BDI-II) and positive and negative affectivity with the Positive and Negative Affect Schedule (PANAS) measured at T1 and T2;
- Anxiety trait in T1 and T2 with the *State Anxiety Inventory* (STAI-A).
- The working memory performance measured in T1 and T2 with the span reversed.
- Inhibitory control evaluated by performance at a Go/Nogo task and its event-related potential (Nogo N2 and Nogo P3). This measurement will be carried out as part of a clinical examination (cognitive and neurophysiological battery with an electroencephalogram) offered to patients during their hospitalization at Unit 72. This review will be conducted before and after the intervention (in T1 and T2).

All the questionnaires were in French version.

Metacognition items:

At the end of the experiment, patients will be asked orally (1) Do you think you are in the active tDCS group?, (2) Would you be interested in continuing this intervention over a longer period of time?

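### The plan describes no masking of those who process and score the Nogo N2/P3 recordings, so the ERP part of the inhibition outcome is open to scorer bias

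*Combined protocol and SAP*

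**What the plan says.** Section 3.1 gives the design: "This will be a randomized, sham-controlled, single-blind study". No section says who is blinded. Two features bear on this:

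- The sham in section 3.3: "Sham group: 0 mA for 20 min, 2 mA for the first 15 and last seconds". Brief current of this kind hides the allocation from the person being stimulated.
- The closing question in section 3.4: "Do you think you are in the active tDCS group". It is put to patients only. No operator, assessor or scorer is asked to guess.

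The secondary outcome at issue is in section 3.4: "Inhibitory control evaluated by performance at a Go/Nogo task and its event-related potential (Nogo N2 and Nogo P3". On its setting the section adds: "This measurement will be carried out as part of a clinical examination (cognitive and neurophysiological battery with an electroencephalogram) offered to patients". Section 3.2 says that "evoked potentials will be acquired for each participant at two points", and places the two batteries "on the Friday preceding (T1) and the Monday following (T2) the intervention week". Section 3.5 analyses the secondary outcomes by mixed ANOVA, Time (T1, T2) by Condition (active, sham).

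The plan does not say who records the EEG, who processes it or what those people know. It describes no coded files, no separate scorer and no preset rule for rejecting artefacts or measuring N2 and P3.

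**The concern.** One of the four hypotheses in section 2 is that stimulation improves inhibition. Its neurophysiological evidence is the change in Nogo N2 and P3 from T1 to T2. Someone has to decide which epochs to reject and how to identify each component, and these decisions leave room for judgement. If that person knows that a file is a post-treatment recording from an active patient, small choices can lean one way. The Time by Condition interaction would then register the lean as a treatment effect.

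Section 3.2 also says the potentials are recorded to study what underlies relapse and abstinence. Follow-up lasts a year, so a scorer working late could know relapse status as well.

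The exposure is avoidable. A stored recording can be scored without knowing whose it is, which is not true of an interview or a supervised session.

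**Working it through.** **Step 1: the plan's own figure.** The plan gives no figure for scorer bias or for the power of the ERP analysis. The only relevant number is the total of 60 (section 3.1). It equals the recruitment forecast in section 3.2: 5 per month × 12 months = 60. This is recruitment capacity and not a power calculation.

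**Step 2: who is masked, by the text.**

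| Role | What the documents say |
|---|---|
| Patient | Sham current (3.3) and allocation guess (3.4) imply masking |
| tDCS operator | Nothing stated |
| Staff running T1 and T2 | Unit 72 clinical examination (3.4); masking not stated |
| N2/P3 processor and scorer | Nothing stated |

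**Step 3: how scorer knowledge reaches the test.** With two visits and two arms, the Time by Condition F test equals the square of a two-sample t test on the T2 − T1 change. A shift applied to all T2 files alike cancels between arms. A shift applied to both visits of one arm cancels within patients. A systematic lean towards one arm's change therefore needs knowledge of both arm and visit, so the code should hide both.

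**Step 4: illustration of size.** Inputs:

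- n = 30 per arm: an assumption. Section 3.1 gives 60 patients in two groups but no ratio.
- Two-sided α = 0.05: an assumption. The plan states no level.
- True effect = 0.
- b, the between-arm scoring shift in SD of the change score: 0.1, 0.2 and 0.3, all assumptions. The documents offer no value.

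Degrees of freedom = 2 × 30 − 2 = 58. Noncentrality = b × √(n/2) = b × √15 = b × 3.873. The false-positive rate is the probability that a noncentral t variable falls outside the two-sided 5% critical values on 58 degrees of freedom.

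| b (SD of change) | Noncentrality | False-positive rate |
|---|---|---|
| 0 | 0 | 5.0% |
| 0.1 | 0.387 | 6.7% |
| 0.2 | 0.775 | 11.9% |
| 0.3 | 1.162 | 20.8% |

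Coded scoring returns the rate to 5% only if the whole shift arises in offline scoring.

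**Step 5: number of files.** 60 patients × 2 visits = 120 recordings, if every patient completes both.

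**The case against.** The strongest reply is that the finding rests on silence. The text does not say that staff know the allocation, or that those who deliver tDCS also test patients or score the EEG. The battery belongs to a clinical examination at Unit 72, so it may be run quite apart from the stimulation sessions. This is fair. A reader might infer that only the patient is blinded, but the documents do not establish it. They support the narrower statement that masking of scorers is not described. That is enough here, because a team following the plan as written would have no duty to mask them.

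Three further limits stand.

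- A reader might infer that coded files would remove the bias. They would not. Instructions and encouragement at T2 happen before any file exists, and a patient who guesses the arm may try harder.
- A reader might extend the argument to Go/Nogo task performance or to the reverse span. The argument here concerns judgement in processing and scoring an ERP, and it does not carry over to counts of task responses. Performance remains exposed to effort and expectation, which coding cannot reach.
- The calculation is generic. Any outcome given the same assumed shift would show the same inflation, so the figures are no evidence that scoring in this trial is biased.

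It can also be said that masking matters more for relapse, the primary outcome, since for follow-up "The call will be made via Unit 72 personnel", with no masking stated. That is true, but it involves a different task and a different remedy. Masking the caller would leave EEG scoring as it is.

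**Conclusion.** The point holds in a limited form and is minor. The trial is called single-blind, the masking described points to the patient, and no section masks the people who process and score Nogo N2 and P3. The ERP part of one secondary outcome is therefore open to scorer bias that a cheap step would reduce.

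The size is unknown. The rise from 5% to about 7%, 12% or 21% rests on assumed shifts of 0.1, 0.2 and 0.3 SD of the change score, 30 patients per arm, a two-sided 5% test and no true effect. The conclusion does not depend on these values: the case for coded scoring is that it costs little and closes one explanation for an N2/P3 difference. It does not touch the primary outcome, the questionnaires or the conduct of the T2 session.

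**What to change.** Add to section 3.4 or 3.5:

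1. T1 and T2 EEG files are renamed with a random code that hides arm and visit, including any recording date visible to the scorer.
2. Rules for artefact rejection and for measuring N2 and P3 are written down before scoring starts.
3. Processing and measurement are completed and locked on the coded files before the key is opened.
4. A team member other than the scorer holds the key.

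Section 3.1 should also say who is blinded. If scorers are already masked in practice, stating so would settle the point.

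The cost is renaming about 120 files, writing the scoring rules, keeping the key closed until the lock, and a few lines of protocol text. An existing team member can hold the key, although the documents do not give the team's size. No patient, visit, treatment or planned test changes. The step can still be adopted after recordings exist, provided they have not yet been scored.

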3.2. Procedure

During the first two weeks of hospitalization, the study will be offered to patients. If they accept, a first semi-structured interview will be organized to explain the study, sign the informed consent, collect more information and verify the inclusion and exclusion criteria. During this interview, the demographic characteristics (age, sex and level of education), history with alcohol (number of years of dependence, number of previous treatment, etc.), frequency and amount of alcohol consumed before treatment, psychiatric history, etc. The DSM 5 criteria will be verified, and patients will complete these questionnaires in French version: *Alcohol Use Disorder Identification Test (AUDIT)*, *Impulsivity Behavior Scale (UPPS-P)* and *Trait Anxiety Inventory (STAI-B)*.

From Monday to Friday of the third week of hospitalization, patients will receive the procedure. Five consecutive 20 minute days of tDCS, either active or sham. Before and after each session, the tie will be measured using analog visual scales. To measure the effects of tDCS, on the Friday preceding (T1) and the Monday following (T2) the intervention week,

patients will respond to a battery of questionnaires and cognitive tasks during the recording of evoked potentials (via an electroencephalogram). T1 and T2 will each last approximately one hour.

Figure 1: Study plan. Day 1 is theoretically the first day of hospitalization and the procedure takes place between Day 15 and 19.

In order to observe whether specific neural changes underlie relapse and abstinence, evoked potentials will be acquired for each participant at two points, before the start of the stimulation by tDCS and once the five sessions have been completed.

Once hospitalization is complete, patients will be followed by telephone call to find out the status of their abstinence and/or alcohol consumption. The call will be made via Unit 72 personnel.

Recruitment would start if possible at the end of March 2021 for a period of 12 months. Based on our estimates based on the performance of the previous study, five patients will be recruited per month.

[figure not shown]
3.3. tDCS

During the neuromodulation session, the patient will watch nature documentaries, cut into 5 episodes of 20 minutes.

The configuration of tDCS is based on recommendations in the literature (Fregni et al., 2020; Lefaucheur et al., 2017).

- 5 sessions of bilateral stimulation of the dlPFC;
- Electrode setup: the anode right on F4 and cathode left on F3, according to international system 10-20 for EEG;
- Administration of 2mA of current for 20 min;
- Sham group: 0 mA for 20 min, 2 mA for the first 15 and last seconds.

Figure 2: Localization of the anode (red) and the cathode (blue) over the dlPFC.

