3.5. Statistical analyses

Primary measurement: In order to respond to our primary assumptions about relapse, we will perform logistic regressions with the independent variable conditions (tDCS active scored 1 and tDCS sham scored -1) and the variable dependent relapse at each measurement (2 weeks, 1 month, 3 months, 6 months and 1 year). A Kaplan-Meier survival analysis will be performed on the number of days prior to relapse to compare the curves up to one year of follow-up.

Finally, in order to compare our two conditions to the four conditions of the previous study, we will perform a logistic regression with linear polynomial contrasts (combined active tDCS with ICT > tDCS only > tDCS sham).

Secondary measures: In order to respond to our secondary assumptions about the variables before and after the intervention, we will perform mixed repeated measures ANOVAs [Time (T1 vs. T2) x Condition (tDCS active vs. tDCS sham)].

4. Benefits

At the individual level, stimulation by tDCS could on the one hand help patients to prolong alcohol abstinence time and on the other have positive effects on mood, especially an improvement in the level of anxiety and depression.

In a broader sense, this study will contribute to a better definition of the mechanisms involved in abstinence and in the phenomenon of relapse of alcohol use disorders. It will also compare whether tDCS is more effective alone or combined with cognitive training. The purpose of this study is to support medical research to improve management for people with alcohol dependence.

5. Safety and tolerability of tDCS

The tolerance of tDCS will be assessed during stimulation with an likert scale. A short questionnaire reporting possible side effects will be distributed to all participants to record the symptoms caused by stimulation.

The most common side effects include tingling, itching, and mild erythema. Although they are less frequent, the perception of a feeling of discomfort or burning, as well as the occurrence of a headache, are also possible events. These are side effects that are well tolerated, essentially limited to the time of stimulation and do not require medical treatment. Severe adverse effects or late onset were not identified.

6. Ethics

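### The primary outcome rests on telephone calls by the treating unit's staff in a single-blind trial, and nothing requires the caller to be unaware of allocation

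*Combined protocol and SAP*

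**What the plan says.** - **Setting and blinding (3.1).** "This is a clinical trial that is part of an alcohol detoxification cure at Unit 72 Addictology of CHU Brugmann". "This will be a randomized, sham-controlled, single-blind study". The section does not name the blinded party or say who holds the allocation.
- **Signs of who is blinded (3.3, 3.4).** The sham group receives brief current at the start and end of each session. At the end of the experiment patients are asked "Do you think you are in the active tDCS group". No such question is put to staff.
- **How the outcome is obtained (3.2).** After discharge, "patients will be followed by telephone call to find out the status of their abstinence and/or alcohol consumption". On who does this: "The call will be made via Unit 72 personnel".
- **What the calls feed (3.4, 3.5).** The primary variables are "Relapse and total abstinence measured at several defined times: two weeks, one month, three months, six months and one year after treatment". The logistic regressions take as outcome "the variable dependent relapse at each measurement (2 weeks, 1 month, 3 months, 6 months and 1 year"). The Kaplan-Meier analysis uses the number of days to relapse over the same year.
- **What is not there.** The plan gives no masking rule for the caller, no separation of callers from tDCS operators, no call script, no definition of relapse, and no biomarker or informant check of drinking after discharge.

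**The concern.** A sham protects against the patient's expectations. It does nothing about a caller who knows the arm. Here the caller comes from the unit where the intervention is given, the outcome is what the patient says on the telephone, and relapse has no written definition. The caller therefore has room both in how far to probe and in how to classify the answer. Under the plan as written, the person who ran the active or sham sessions could make the calls.

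The relapse hypothesis in section 2 concerns two weeks after treatment. If allocation is known to the caller, a difference at that time could not be told apart from a difference in questioning or recording, and no later analysis could repair it. The same process produces all five time points, so the problem could recur at each.

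**Working it through.** **1. Does any text mask the caller?**

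| Question | Where it would be answered | Finding |
|---|---|---|
| Who is blinded? | 3.1 | Single-blind, party not named |
| Who delivers tDCS? | 3.3 | Not stated |
| Who makes the calls? | 3.2 | Unit 72 personnel |
| Must the caller be unaware of allocation? | 3.2, 3.4 | Not addressed |
| Is reported drinking after discharge checked? | 3.2, 3.4, Table 1 | No check described |
| Is relapse defined? | 3.4, 3.5 | No |

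The plan therefore permits an unmasked tDCS operator to collect the primary outcome. It does not say that this will happen.

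**2. The plan's own figure.** The only design figure is the total of 60, which equals the recruitment forecast in 3.2: 5 per month × 12 months = 60. There is no alpha, power or effect size to reproduce.

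**3. Illustration of size.** Inputs:
- n = 30 per arm: assumed, since 60 are divided into two groups but no ratio is given.
- True relapse p = 0.50 or 0.70 in both arms (no true effect): assumed.
- Share f of active-arm relapses not recorded = 0, 0.10 or 0.20, with none missed under sham: assumed.

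Recorded relapse in the active arm is p(1 − f). The apparent odds ratio is [p(1 − f) / (1 − p(1 − f))] ÷ [p / (1 − p)].
- p = 0.50, f = 0.10: (0.45/0.55) ÷ 1 = 0.82
- p = 0.50, f = 0.20: (0.40/0.60) ÷ 1 = 0.67
- p = 0.70, f = 0.10: (0.63/0.37) ÷ (0.70/0.30) = 0.73
- p = 0.70, f = 0.20: (0.56/0.44) ÷ (0.70/0.30) = 0.55

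The false-positive rate is the sum, over all pairs (a, s) with a two-sided p-value at or below 0.05, of Bin(a; 30, p(1 − f)) × Bin(s; 30, p). The likelihood-ratio test corresponds to the planned logistic regression with one binary predictor.

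| True relapse | Missed in active arm | Likelihood-ratio | Fisher's exact |
|---|---|---|---|
| 50% | 0 | 5.2% | 2.7% |
| 50% | 10% | 7.0% | 3.9% |
| 50% | 20% | 12.5% | 7.7% |
| 70% | 0 | 5.8% | 2.6% |
| 70% | 10% | 9.6% | 5.1% |
| 70% | 20% | 20.9% | 13.3% |

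The right comparator in each block is its own zero row, not a nominal 5%.

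**4. In patients.** The expected number of missed relapses is 30 × p × f. That is 1.5 and 3.0 at 50% relapse, and 2.1 and 4.2 at 70%. Starting from 15/30 in both arms, eight relapses recorded as abstinent in one arm give 15/30 against 7/30. This is nominally significant by the likelihood-ratio test (p = 0.031) but not by Fisher's exact test (p = 0.060).

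**The case against.** The strongest reply is that the documents never say a caller knows the allocation. That is correct. Single-blind is the only description given, and no text says who delivers tDCS. Section 3.1 presents the stimulation as added to the unit's usual management, so the callers could be ward staff with no part in the sessions.

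A reader might infer more than the text supports, in four ways:
- **That unit staff are unblinded.** This is inferred from the sham and the patient-only question. Even if the patient is the one blinded party, it does not follow that every member of the unit knows the arms.
- **That the result is biased toward active tDCS.** This needs a caller who knows the arm and who also questions or records differently by arm. Neither is documented. The direction is only what one might expect from a caller who shares the hypotheses in section 2.
- **That nothing in the trial is measured objectively.** Section 3.4 includes Go/Nogo performance with event-related potentials and a reverse memory span. The gap concerns drinking after discharge only.
- **That the error rates above are evidence.** The arm sizes, relapse rates and under-recording are all assumed, all misrecording is placed in one arm, and the rates depend on the test.

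What stands against the objection is that the plan also does not say callers are unaware of allocation. Silence on this point leaves the primary outcome unprotected.

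**Conclusion.** The point holds as a gap in protection. The primary outcome comes only from telephone calls by the treating unit's staff, in a trial that names no masked staff, with no bar on the tDCS operator making the calls. Relapse could be elicited or recorded differently by arm. Whether it would be, and in which direction, cannot be known from the documents.

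Confidence is high that the safeguard is absent, and only moderate that its absence would distort the result. Under the assumed scenarios, missing one relapse in ten in one arm inflates the error rate modestly, and missing one in five roughly doubles to quadruples it on the likelihood-ratio scale (12.5/5.2 = 2.4; 20.9/5.8 = 3.6). The change should be made because it is cheap and the flaw cannot be corrected after the data are collected.

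**What to change.** In 3.2, replace "The call will be made via Unit 72 personnel" with:

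> Follow-up calls are made by a Unit 72 staff member who did not deliver the tDCS sessions and has no access to the allocation list, using a fixed script (any drinking since last contact, date of first drink, drinks per day). Relapse and abstinence are classified from the recorded answers by one pre-stated definition before allocation is disclosed.

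In 3.1, state who is blinded: patients, and the callers for the follow-up relapse outcome only. Labelling the whole trial outcome-assessor-blind would claim too much, because the change masks only these calls and not, for example, the craving ratings taken around each session.

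The definition of relapse has to be written by the investigators, since the script alone does not supply one. The date of first drink also supports the planned analysis of days to relapse. The change adds no objective verification of drinking.

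**Cost.** Two edited passages, a short script and a rota constraint, because the tDCS operator cannot make the calls. This assumes the unit has another member of staff available; the documents do not describe staffing.
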